Listings by patient (ordered by dose level): start date and stop date of each dosing period within each cycle (including records with 0mg), administered total daily dose for each period, any missed doses with unknown dates (yes/no), number of missed doses with unknown dates, reason for any dosing changes will be provided.

Listings by subject and each cycle (ordered by dose level): cycle length, total planned dose, administered total dose, percentage of planned dose, dose delay (yes/no), dose reduction (yes/no), and dose interruption (yes/no) will be provided.

Prior, Concomitant, and Further Therapies

Prior, concomitant, and further therapies (drug and non-drug treatments) will be coded by the World Health Organization (WHO) medical dictionary. Listings of prior, concomitant, and further therapies will be provided separately.

11. APPENDICES

11.1. APPENDIX 1: CATEGORICAL CLASSES FOR ECG AND VITAL SIGNS

Categories for QTcF

QTcF(ms)	450 < max. < 480	481 < max. < 500	max. > 501
QTcF(ms) change from baseline	30 < max. ' .S60	max. > 60	

Categories for PR and QRS

PR(ms)	max > 300	
PR (ms) increase from baseline	Baseline > 200 and max. > 25% increase	Baseline ' .S200 and max. c:::50% mcrease
QRS (ms)	max > 200	
QRS (ms) increase from baseline	Baseline > 100 and max. > 25% increase	Baseline ' .S100 and max. c:::50% mcrease

Categories for Vital Signs

Svstolic BP (mm Hg)	min. < 90	
Systolic BP (mm Hg) change from baseline	max. decrease c:::30	max. increase c:::30
Diastolic BP (mm Hg)	min. < 50	
Diastolic BP (mm Hg) change from baseline	max. decrease c:::20	max. increase c:::20
Supine pulse rate (born)	min. < 40	max. > 120

Measurements that fulfil these criteria are to be listed in the study report.

11.2. APPENDIX 2: RECIST (Response Evaluation Criteria In Solid Tumors) version 1.1 Guidelines

Adapted from E.A. Eisenhauer, et al: New response evaluation criteria in solid tumours: Revised RECIST guideline (version 1.1). European Journal of Cancer 45 (2009) 228-247

CATEGORIZING LESIONS AT BASELINE

Measurable Lesions

- Lesions that can be accurately measured in at least one dimension.
- Lesions with longest diameter twice the slice thickness and at least 10 mill or greater when assessed by CT or MRI (slice thickness 5-8 mm).
- Lesions with longest diameter at least 20 mm when assessed by Chest X-ray.

- Superficial lesions with longest diameter 10 mm or greater when assessed by caliper.
- Malignant lymph nodes with the short axis 15 mm or greater when assessed by CT.

NOTE: The shortest axis is used as the diameter for malignant lymph nodes, longest axis for all other measurable lesions.

Non-measurable disease

Non-measurable disease includes lesions too small to be considered measurable (including nodes with short axis between 10 and 14.9 mm) and truly non-measurable disease such as pleural or pericardial effusions, ascites, inflammatory breast disease, leptomeningeal disease, lymphangitic involvement of skin or lung, clinical lesions that cannot be accurately measured with calipers, abdominal masses identified by physical exam that are not measurable by reproducible imaging techniques.

- Bone disease: Bone disease is non-measurable with the exception of soft tissue components that can be evaluated by CT or MRI and meet the definition of measurability at baseline.
- Previous local treatment: A previously irradiated lesion (or lesion subjected to other local treatment) is non-measurable unless it has progressed since completion of treatment.

Normal sites

- Cystic lesions: Simple cysts should not be considered as malignant lesions and should not be recorded either as target or non-target disease. Cystic lesions thought to represent cystic metastases can be measurable lesions, if they meet the specific definition above. If non-cystic lesions are also present, these are preferred as target lesions.
- Normal nodes: Nodes with short axis <10 mm are considered normal and should not be recorded or followed either as measurable or non-measurable disease.

Recording Tumor Assessments

All sites of disease must be assessed at baseline. Baseline assessments should be done as close as possible prior to study start. For an adequate baseline assessment, all required scans must be done within 28 days prior to randomization and all disease must be documented appropriately. If baseline assessment is inadequate, subsequent statuses generally should be non-evaluable.

Target Lesions

All measurable lesions up to a maximum of 2 lesions per organ, 5 lesions in total, representative of all involved organs, should be identified as target lesions at baseline. Target lesions should be selected on the basis of size (longest lesions) and suitability for accurate repeated measurements. Record the longest diameter for each lesion, except in the case of pathological lymph nodes for which the short axis should be recorded. The sum of the diameters (longest for non-nodal lesions, short axis for nodal lesions) for all target lesions at baseline will be the basis for comparison to assessments performed on study.

- If two target lesions coalesce the measurement of the coalesced mass is used. If a large target lesion splits, the sum of the parts is used.
- Measurements for target lesions that become small should continue to be recorded. If a target lesion becomes too small to measure, 0 mm should be recorded if the lesion is considered to have disappeared; otherwise a default value of 5 mm should be recorded.

NOTE: When nodal lesions decrease to <10 mm (nodal), the actual measurement should still be recorded.

Non-target Disease

All non-measurable disease is non-target. All measurable lesions not identified as target lesions are also included as non-target disease. Measurements are not required but rather assessments will be expressed as CR, Non-CR/Non-PD, PD, Non-evaluable (NE). Multiple non-target lesions in one organ may be recorded as a single item on the case report form (eg, 'multiple enlarged pelvic lymph nodes' or 'multiple liver metastases').

OBJECTIVE RESPONSE STATUS AT EACH EVALUATION

Disease sites must be assessed using the same technique as baseline, including consistent administration of contrast and timing of scanning. If a change needs to be made the case must be discussed with the radiologist to determine if substitution is possible. If not, subsequent objective statuses might be non-evaluable.

Target Disease

1. Complete Response (CR): Complete disappearance of all target lesions with the exception of nodal disease. All target nodes must decrease to nodal size (short axis <10 mm). All target lesions must be assessed.
2. Partial Response (PR): Greater than or equal to 30% decrease under baseline of the sum of diameters of all target measurable lesions. The short diameter is used in the sum for target nodes, while the longest diameter is used in the sum for all other target lesions. All target lesions must be assessed.

3. Stable: Does not qualify for CR, PR or Progression. All target lesions must be assessed. Stable can follow PR only in the rare case that the sum increases by less than 20% from the nadir, but enough that a previously documented 30% decrease no longer holds.
4. Objective Progression (PD): 20% increase in the sum of diameters of target measurable lesions above the smallest sum observed (over baseline if no decrease in the sum is observed during therapy), with a minimum absolute increase of 5 mm.
5. Non-evaluable (NE): Progression has not been documented, and
 - One or more target measurable lesions have not been assessed; or
 - One or more target lesions cannot be measured accurately (eg, poorly visible unless due to being too small to measure); or
 - One or more target lesions were excised or irradiated.

Non-target disease

6. CR: Disappearance of all non-target lesions and normalization of tumor marker levels. All lymph nodes must be 'nonnal' in size (<10 mm short axis).
7. Non-CR/Non-PD: Persistence of any non-target lesions and/or tumor marker level above the nonnal limits.
8. PD: Unequivocal progression of pre-existing lesions. Generally the overall tumor burden must increase sufficiently to merit discontinuation of therapy. In the presence of SD or PR in target disease, progression due to unequivocal increase in non-target disease should be rare.
9. NE: Progression has not been determined and one or more non-target sites were not assessed or assessment methods were inconsistent with those used at baseline.

New Lesions

The appearance of any new unequivocal malignant lesion indicates PD. If a new lesion is equivocal, for example due to its small size, continued assessment will clarify the etiology. If repeat assessments confirm the lesion, then progression should be recorded on the date of the initial assessment. A lesion identified in an area not previously scanned will be considered a new lesion.

Supplemental Investigations

- If CR determination depends on a residual lesion that decreased in size but did not disappear completely, it is recommended the residual lesion be investigated with biopsy or fine needle aspirate. If no disease is identified, objective status is CR.

- If progression determination depends on a lesion with an increase possibly due to necrosis, the lesion may be investigated with biopsy or fine needle aspirate to clarify status.

Subjective Progression

Patients requiring discontinuation of treatment without objective evidence of disease progression should not be reported as PD on tumor assessment CRFs. This should be indicated on the end of treatment CRF as off treatment due to Global Deterioration of Health Status. Every effort should be made to document objective progression even after discontinuation of treatment.

Table 4 Objective Response Status at each Evaluation

Target Lesions	Non-target Disease	New Lesions	Objective status
CR	CR	No	CR
CR	Non-CR/Non-PD	No	PR
CR	NE or Missing	No	PR
PR	Non-CR/Non-PD, NE or Missing	No	PR
SD	Non-CR/Non-PD, NE or Missing	No	Stable
NE or Missing	Non-PD	No	NE
PD	Any	Yes or No	PD
Any	PD	Yes or No	PD
Any	Any	Yes	PD

If the protocol allows enrollment of patients with only non-target disease, the following table will be used:

Table 5 Objective Response Status at each Evaluation for Patients with Non-Target Disease Only

Non-target Disease	New Lesions	Objective status
CR	No	CR
Non-CR/Non-PD	No	Non-CR/Non-PD
NE	No	NE
Unequivocal progression	Yes or No	PD
Any	Yes	PD

Best Overall Response

The best overall response (BOR) is the best response recorded from the randomization until disease progression or death due to any cause. This is derived from the sequence of objective

statuses. Objective statuses are not considered after objective progression is documented or after start of the first anticancer treatment post discontinuation of protocol treatment. BOR for each patient will be derived as one of the following categories.

- **Complete response (CR):** At least one objective status of CR documented before progression.
- **Partial response (PR):** At least one objective status of PR documented before progression.
- **Stable disease (SD):** At least one objective status of stable documented at least 8 weeks after randomization date and before progression but not qualifying as CR, PR.
- **Progressive Disease (PD):** Objective status of progression within 16 weeks of randomization, not qualifying as CR, PR or SD.
- **Non-evaluable (NE):** Progression not documented within 16 weeks after randomization and no other response category applies.

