		
Section 5 Study Treatments: Listed letrozole and fulvestrant as investigational products rather than standard of care.
 
 Section 5.2 Patient Compliance: Indicated that fulvestrant will be administered at the investigational site and PF-06873600 and letrozole will be distributed to the patient. Section 5.3 Investigational Product Supplies: Indicated that letrozole and fulvestrant will be supplied by Pfizer, Section 5.3.1.1 PF-06873600: Updated strengths for the immediate and modified-release (MR) tablets and added details regarding table counts. Section 5.3.1.2 Letrozole: Removed “and Fulvestrant” from section title. Added new section: Section 5.3.1.3 Fulvestrant Section 5.4.1, PF-06873600: Added bullet for Part 1D only. Added instructions for the administration of letrozole and fulvestrant. Section 5.4.2. 5.4.2.2. Requirements for the Food Effect Cohort (Part 2 Arm A): Replaced Arm B with Arm A. Added new section: 5.4.3.2 Dose Interruption of Patients with Presumed or Active COVID-19/SARs-CoV2 Infection. Section 5.4.3.4 Dose Reductions: Added instructions for patients in Part 1D and added that at the discretion of the investigator or Sponsor based on emerging safety data patients may be asked to reduce their dose within the DLT window. Table 3 Dose Modifications for PF-06873600-Related Toxicity. Added instructions for patients in

Document	Version Date	Summary of Changes and Rationale
		Part 1D with Grade 3 nonhematologic and hematologic toxicities.
		Section 6.4: Updated text regarding permanent discontinuation of study intervention and the study with text to comply with updated protocol template language effective December 2019/May 2020.
		
CCI [REDACTED]
 
I [REDACTED]
 
I [REDACTED]
 
I [REDACTED]
 
I [REDACTED]

		
Section 8 Adverse Event Reporting
 
 Section 8.1.4 Time Period for Collecting AE/SAE Information: Added details for long-term follow-up collection period for Part 2 only.
		Sections 9.2.2/9.3.1/9.3.2 Part 1 and Part 2: Updated number of patients to be enrolled.
		Section 9.5.1.1 Single Dose and Steady State PF 06873600 Pharmacokinetic Analysis: Added PK sampling for patients in Part 1D added specifics for samples on C2D8.
		Appendix 4. RECIST (Response Evaluation Criteria In Solid Tumors) version 1.1 Guidelines: Best Overall Response section, Stable disease bullet: changed timing after randomization from 8 weeks to 6 weeks.

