Appendix 8. Study Procedures After Primary Completion Date (PCD) Until End of
Trial..... 182

SCHEDULE OF ACTIVITIES (PART 1, PART 2 AND J-LIC)

The schedule of activities table provides an overview of the protocol visits and procedures. Refer to the [ASSESSMENTS](#) section of the protocol for detailed information on each assessment required for compliance with the protocol.

The investigator may schedule visits (unplanned visits) in addition to those listed in the schedule of activities in order to conduct evaluations or assessments required to protect the well-being of the patient.

See [Appendix 6](#) for alternative measures during public emergencies including the COVID-19 pandemic.

Protocol Activity	Screening	Active Treatment Phase [†] - One Cycle = 28 days					End of Treatment/ Withdrawal [§]	Post-Treatment Follow-Up [*]
		Cycles 1 and 2			Cycles ≥3			
Study Day	Within 28 days prior to registration unless specified otherwise	Day 1 [‡]	Day 8	Day 15	Day 21	Day 1		
Visit Window				±3 days	±3 days	±3 days	±5 days	
Informed Consent ¹	X							
Medical/Oncological History ²	X							
Baseline Signs/Symptoms ³		X						
Physical Examination ⁴	X						X	
Abbreviated Physical Examination ⁵		X	X	X	X	X		X
Vital Signs ⁶	X	X	X	X	X	X	X	X
Contraception Check ⁷	X	X				X	X	
ECOG Performance Status ⁸	X	X				X	X	X
12-Lead ECG ⁹	X	X	X C1 ⁹ and C2 ⁹	X C1 only		X	X	
Laboratory Studies¹⁰								
Hematology	X	X	X	X	X	X	X	(X)
Blood Chemistry	X	X	X ¹¹	X ¹¹	X ¹¹	X	X	(X)
Coagulation	X	X						(X)
Urinalysis	X						X	(X)
Pregnancy test	X	X				X	X	
Viral disease screening ¹²	X							
Disease Assessment								
Tumor markers (for breast cancer: CA 15-3 and CEA; Part 1 only for ovarian cancer: CA 125)	X	X				X	X	
CT/MRI Scans of Chest, Abdomen, Pelvis, any clinically indicated sites of	X	Performed every 8 weeks from C1D1 (±7 days) for the first 6 months, and then every 12 weeks (±7 days)					X ¹³	

Protocol Activity	Screening	Active Treatment Phase [†] - One Cycle = 28 days					End of Treatment/ Withdrawal [§]	Post-Treatment Follow-Up [*]
		Cycles 1 and 2				Cycles ≥3		
Study Day	Within 28 days prior to registration unless specified otherwise	Day 1 [‡]	Day 8	Day 15	Day 21	Day 1		
Visit Window			±3 days	±3 days	±3 days	±5 days		±7 days
disease, and of bone lesions; Clinical evaluation of superficial disease ¹³ Follow up for Overall Survival (OS)		thereafter for up to 2 years. After 2 years, performed every 4 months thereafter.						
Study Treatment								

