- If CR determination depends on a residual lesion that decreased in size but did not disappear completely, it is recommended the residual lesion be investigated with biopsy or fine needle aspirate. If no disease is identified, objective status is CR.
- If progression determination depends on a lesion with an increase possibly due to necrosis, the lesion may be investigated with biopsy or fine needle aspirate to clarify status.

Subjective Progression

Patients requiring discontinuation of treatment without objective evidence of disease progression should not be reported as PD on tumor assessment CRFs. This should be indicated on the end of treatment CRF as off treatment due to Global Deterioration of Health Status. Every effort should be made to document objective progression even after discontinuation of treatment.

Table 5. Objective Response Status at each Evaluation

Target Lesions	Non-target Disease	New Lesions	Objective status
CR	CR	No	CR
CR	Non-CR/Non-PD	No	PR
CR	NE or Missing	No	PR
PR	Non-CR/Non-PD, NE or Missing	No	PR
SD	Non-CR/Non-PD, NE or Missing	No	Stable

Table 5. Objective Response Status at each Evaluation

Target Lesions	Non-target Disease	New Lesions	Objective status
NE or Missing	Non-PD	No	NE
PD	Any	Yes or No	PD
Any	PD	Yes or No	PD
Any	Any	Yes	PD

If the protocol allows enrollment of patients with only non-target disease, the following table will be used:

Table 6. Objective Response Status at each Evaluation for Patients with Non-Target Disease Only

Non-target Disease	New Lesions	Objective status
CR	No	CR
Non-CR/Non-PD	No	Non-CR/Non-PD
NE	No	NE
Unequivocal progression	Yes or No	PD
Any	Yes	PD

Best Overall Response

The best overall response (BOR) is the best response recorded from the randomization until disease progression or death due to any cause. This is derived from the sequence of objective statuses. Objective statuses are not considered after objective progression is documented or after start of the first anticancer treatment post discontinuation of protocol treatment. BOR for each patient will be derived as one of the following categories.

- **Complete response (CR):** At least one objective status of CR documented before progression.
- **Partial response (PR):** At least one objective status of PR documented before progression.
- **Stable disease (SD):** At least one objective status of stable documented at least 6 weeks after randomization date and before progression but not qualifying as CR, PR.

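### The SAP sets the stable-disease minimum at 8 weeks and the protocol at 6, so a patient stable only on an on-schedule scan at days 49 to 55 is labelled PD or NE instead of SD

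*SAP*

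**What the plan says.** The two RECIST appendices give different minimum times for the same BOR category.

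- SAP Appendix 2 (Section 11.2), stable disease: "At least one objective status of stable documented at least 8 weeks after randomization date and before progression".
- Protocol Appendix 4, stable disease: "At least one objective status of stable documented at least 6 weeks after randomization date and before progression".

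The neighbouring categories match in the two documents. In the SAP, PD is "Objective status of progression within 16 weeks of randomization, not qualifying as CR, PR or SD", and NE is "Progression not documented within 16 weeks after randomization and no other response category applies".

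The Schedule of Activities in the protocol sets imaging as "Performed every 8 weeks from C1D1 (±7 days) for the first 6 months".

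BOR is a planned output. SAP Sections 7.1 and 9.2.2.1 list it per patient, and Section 9.2.2.1 names it with ORR and DOR as a response-based metric.

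On history only, the August 2020 entry in the protocol's amendment log reads "Stable disease bullet: changed timing after randomization from 8 weeks to 6 weeks". SAP version 2.0 (September 2019) predates that entry. Version 4.0 (March 2023) says it takes in changes through Amendment 9, and its change summary says nothing about keeping 8 weeks.

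**The concern.** Both appendices are current text, and they can give the same patient two different BORs from the same scans. The 8-week limit equals the nominal date of the first scan, so it leaves no room for the early half of the permitted window. A scan done on time but a few days before day 56 cannot support SD under the SAP.

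The result can also look odd. A patient with two evaluable scans, one stable and one showing progression, may be reported as non-evaluable.

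The time origin adds a second problem. Both appendices count from randomization, and the trial is non-randomized. The effect depends on which date a programmer substitutes, so two programmers could derive different BORs.

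The Part 2 arms are planned at about 40, 30 and 30 patients. With arms of that size, a few moved patients would be visible in the SD, PD and NE rows.

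**Working it through.** There is no plan figure to reproduce; this is a check of definitions against the scan calendar. Days are days elapsed since C1D1 unless stated otherwise.

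**Inputs**

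- First scan (Protocol Schedule of Activities): 8 × 7 = 56, ±7, so days 49 to 63, which is 15 whole days.
- Second scan (same source): 16 × 7 = 112, ±7, so days 105 to 119, which is 15 whole days.
- SD limit: SAP 8 × 7 = 56; protocol 6 × 7 = 42.
- PD/NE boundary (both documents): 16 × 7 = 112.

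**Step 1. First-scan days too early to count as SD.** Under the SAP, days 49 to 55 fall short of 56: 7 of 15 permitted days. Under the protocol, none does, because 49 exceeds 42.

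**Step 2. BOR for a patient stable at days 49 to 55, with no response.**

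| What follows | SAP | Protocol |
|---|---|---|
| Progression at second scan, days 105–112 (8 of 15 days) | PD | SD |
| Progression at second scan, days 113–119 (7 of 15 days) | NE | SD |
| No further scan | NE | SD |
| Second scan also stable | SD | SD |

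In the last row the second stable status falls at day 105 or later, which is beyond 56.

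**Step 3. All permitted pairs of scan days, stable then progression.** There are 15 × 15 = 225 pairs. Under the SAP:

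- PD: 7 × 8 = 56 pairs (24.9%)
- NE: 7 × 7 = 49 pairs (21.8%)
- SD: 8 × 15 = 120 pairs (53.3%)

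Under the protocol's 6 weeks all 225 are SD. These percentages are shares of permitted day pairs. Turning them into patient rates would need a distribution of scan days, which the documents do not give.

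**Step 4. Dependence on the origin.** If the clock starts g days before C1D1, a first scan on day d fails the SAP limit when d + g < 56. The number of failing days is max(0, 7 − g): 7 of 15 for g = 0, 4 of 15 for g = 3, and 0 for g of 7 or more.

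**Step 5. Other endpoints.** ORR counts CR and PR (SAP Section 7.1). PFS, DOR and TTP run on progression, death and the censoring rules of SAP Appendix 3. None of them uses the SD limit.

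**The case against.** The best case for leaving the text alone has four parts.

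1. *The SAP may differ.* Protocol Section 9 lets the SAP modify the protocol where appropriate and asks for an amendment only for major changes to primary endpoint definitions or analyses, which SD is not. Neither document justifies its value, and 8 weeks does equal the nominal scan interval. This stands to the extent that 6 weeks is not shown to be the better standard, so a reader should not infer that the SAP is proven to bias disease stabilisation downwards. What remains is an unexplained disagreement, in a SAP that says it is aligned with the amended protocol.

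2. *Few patients may be affected.* A reader might infer that on-schedule stable disease in general is reclassified, or that about half of early progressors are. The documents support neither. A first scan on day 56 or later, a second stable scan or a response gives the same BOR under both rules. An even spread of scan days is also unsupported. A footnote to the Part 1 sampling schedule ties Cycle 3 Day 1, which is 2 × 28 = 56 days after C1D1, to the first on-treatment tumour assessment. That points to clustering near the nominal date, and a scan on exactly day 56 passes.

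3. *The main results do not move.* A reader might infer that the Part 2 activity result is at risk. It is not: that result rests on ORR. SAP Table 3 has no row for SD or disease control.

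4. *The origin is nearly settled.* SAP Section 7.1 already runs overall response from first dose and PFS from C1D1. This stands in part. Appendix 2 still says randomization for the SD, PD and NE limits, and Section 7.1 itself uses that word for TTP.

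**Conclusion.** The inconsistency is real and sits in current text. Counted from C1D1, 7 of the 15 permitted first-scan days meet the protocol's SD minimum and fail the SAP's. A patient is affected only if the sole stable status falls on days 49 to 55 and no later stable scan or response follows.

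The number of such patients cannot be estimated from the documents. The conclusion assumes that C1D1 is the origin; a date 7 or more days earlier would remove the effect. The reach is confined to three categories of one response output, so this is a small but definite error of specification that should be settled before BOR is derived.

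**What to change.** In SAP Appendix 2, change the SD minimum from 8 weeks to 6 weeks, to agree with Protocol Appendix 4. With 42 days, no permitted first-scan day falls short. If 8 weeks is intended, give the reason and state that a stable status on an in-window scan from day 49 counts.

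In the same place, define the origin for the SD, PD and NE limits as C1D1 (first dose), in line with the response and PFS definitions in SAP Section 7.1.

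Both edits are to SAP wording and need no new data. Protocol Appendix 4 carries the same randomization wording. That can be corrected at any further amendment and need not prompt one, since the sponsor decided in September 2022 to terminate the study and primary completion was set for around 5 April 2023.
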